2.4 Primary endpoint/outcome

Health promoting practices by Personal Advisors

- 2.5 Secondary endpoints/outcomes
- Impact on Care Leavers' Health and Wellbeing
- Costs and benefits

Intervention outcome measures

- 2.6 Intervention outcome measures Personal Advisors
- Health promoting practices by Personal Advisors data from semi-structured interviews
 - 2.7 Intervention outcome measures Care Leavers
- Wellbeing 3 questions about Personal Wellbeing based on those used in the ONS Survey
- Physical Health –3 questions about Physical Health from the Census
- Quality of Life one of the following: the ReQOL20; the ReQOL10 or the EQ-5D-5L
- Confidence in health professionals 10-item questionnaire: Revised Perceived Efficacy in Patient-Physician Interactions Questionnaire (PEPPI-10)
- Perceptions of physician empathy 5-item questionnaire concerning perceptions of the PA's empathic qualities in relation to health
- Psychological Coping (Mastery) 7-item questionnaire: Pearlin Mastery Scale
- Health service usage Health Service Use Questions

3 TRIAL DESIGN

The LIFT study is designed as a single-blinded, cluster-randomised trial in which up to 12 groups of Personal Advisors will be randomly allocated to one of two trial arms.

Groups may be teams, local authorities, or groups within a team, depending on the organisational structure of the participating local authorities. We aim to randomise groups of comparable sizes.

Those allocated to the intervention group will receive the training intervention designed in Phase 1. Those allocated to the control arm will not receive the training and will continue to work with Care Leavers 'as usual'.

Prior to randomization, PAs will complete a survey covering the main focus of their work with PAs, their knowledge about public health issues relevant to CLs, and their knowledge of relevant local services.

At 24- and 48-weeks post-training of personal advisors in the experimental arm, follow up data will be collected by researchers unaware of the allocation status of care leavers and personal advisors.

Health service usage data will be collected at two-months intervals from baseline to 52-weeks

Month	Project activity	
1	Briefing of site personnel	
	Identification of Skills Workshop Facilitators	
2	Recruitment of Personal Advisors (PAs)	
2-6	Recruitment of Care Leavers (CLs)	
	Baseline data collection from PAs and CLs	
5-6	Randomisation of PA groups	
5-7	Training of PAs in the Experimental Arm	
	Post-Training Survey of PAs in the Experimental Arm	
7-17	Bimonthly resource use data collection	
10-12	24-week data collection from Care Leavers (Outcome data) 24-week data collection from Personal Advisors (Process and Implementation data)	
17-19	48-week data collection from Care Leavers (Outcome data) 24-week data collection from Personal Advisors (Process and Implementation data)	
14-20	Data analyses	
18-22	Drafting of the report	
22	Consultation on findings	
22-24	Finalising report	

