2.2 Primary objective

To ascertain the feasibility of key procedural elements that would need to form part of an experimental evaluation of the effectiveness of the training intervention, including:

- Whether it is possible to recruit, train and retain all PAs in each participating authority.
- Whether it is possible to recruit and retain a sample of CLs in each arm of the study to a 12 month follow up.
- Whether it is possible to secure blinding of outcome assessors.

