2.3 Secondary objectives

Secondary objectives are to:

- Establish the acceptability and feasibility (data burden and cost), and the factors influencing the completion of measures at baseline (PAs and CLs), post training (PAs) and follow up (PAs and CLs).
- To collect outcome measures and assess their performance and quality with this population (acceptability, completeness, means, variability and distribution of scores).
- To use the data collected to estimate the Intra-cluster Correlation Coefficient (ICC) to inform the sample size require for the main trial.
- Determine the feasibility + cost of accessing and using administrative data, if available
- Ascertain the acceptability to LAs and PAs of randomization
- Consider the implications of any contamination between the two arms of the trial e.g. PAs moving between teams in different trial groups.
- Identify barriers + facilitators to implementation of, and fidelity to, the intervention.
- To use the information gathered to inform the design of a pragmatic trial, if this seems feasible.

Outcome and outcome measures - Feasibility

Outcome 1: Recruitment of care leavers to the study

- Measurement: Count of care leavers randomised
- Timepoint: Feasibility study recruitment period for care leavers
- Outcome 2: Retention of care leavers
 - Measurement: Proportion of recruited care leavers who complete the study assessments
 - o Timepoints: 16, 32 and 48 post intervention
- Outcome 3: Blinded assessment
 - Measurement: Ask assessors to record whether the interviewee has an intervention or control PA - best guess if don't know (two-alternative forced choice).

- Timepoints: 16, 32 and 48 weeks post intervention
- Outcome 4: Recruitment of personal assistants
 - Measurement: Count of personal assistants recruited
 - o Timepoint: Feasibility study recruitment period for personal advisors
- Outcome 5: Fidelity to allocation
 - Measurement: Proportion of recruited personal advisors in intervention group who complete the training
 - o Timepoint: Feasibility study training period for personal advisors
- Outcome 6: Retention of personal advisors
 - Measurement: Proportion of recruited personal advisors who complete the study assessments
 - o Timepoints: post-training, 24 and 48 weeks

Intervention outcomes

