6.7 Qualitative assessments

Care Leavers: At 24- and 48 weeks following the completion of training by PAs, we will collect qualitative data from our sample of care leavers on the extent to which they feel their health needs (including emotional health and wellbeing) have been recognized and addressed by their PAs in the previous six months. The interviews will explore how often they have seen their PA; whether PAs have brought up topics covered in training modules (including help seeking, smoking, alcohol and substance use, sexual health, nutrition and exercise); what their own health and wellbeing concerns are and whether or not they have felt able to bring these to the attention of their PA; what the response was, and how helpful their PA has been more generally in helping them to address their health issues. We will also enquire how the CL feels about health issues being raised by the PA, and whether or not they subsequently took any steps to address them.

At the 48 weeks interview we will also ask care leavers about their experiences of participating in the trial, and what their advice would be to a research team wanting to conduct a larger study. A particular focus of this conversation will be their views on the use of peer researchers, the incentives offered; what information they would want to know about the findings of the trial, and in what format.

All interviews with Care Leavers will be conducted via a conference facility or via Smartphone facility, unless and until circumstances change and face-to-face meetings are judged safe and appropriate.

Personal Advisors: At the 24- and 48- week follow up points we will re-interview the same PAs to explore:

- Frequency and content of contacts with CL, with particular focus on module topics;
- which modules have been most, and least, useful; how or why;
- what factors beyond the training have helped them to develop and implement a focus on health promotion activities with care leavers, and what factors have impeded this (factors to be explored

include organisational factors such as supervision, workload, follow-up support; personal factors such as lack of confidence, adverse experiences, and care leaver attributed factors such as lack of interest, refusal to discuss).

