6.11 Blinding

Peer researchers will not be told the allocation of the care leavers they interview.

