8.3.1 Measuring fidelity

We will run reports on participants' completion of the of the online modules and attendance at webinars and the Skills Workshop. The facilitators of the Skills Workshop will work to a prescribed manual and information will be collected on the extent to which the schedule was adhered to. Some workshops will be observed by a member of the research team.

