12.4 Patient and Public Involvement (PPI)

The views of young people are central to this study and have played a significant role in its development. The research team include peer researchers who are full members of the Trial Management Group (known in this study as the Programme Management Group). The peer researchers are supported by Coram Voice, and they have been involved in developing all aspects of the training intervention, the development of Participant information Leaflets and Consent Forms, and the choice of outcomes and outcome measures. They will collect outcome data at the two follow-up points from care leavers and contribute to the interpretation of the data analyses and drafting of the final report and other papers (see Publications Policy Section 15).

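### The claim of blinded follow-up cannot hold for the Personal Advisor interviews, and the care-leaver blinding check cannot separate leaked allocation from cues in the interview

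*Protocol*

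**What the plan says.** Section 3 calls the trial single-blinded and says that at 24 and 48 weeks after training "follow up data will be collected by researchers unaware of the allocation status of care leavers and personal advisors". The claim covers both participant groups. Section 2.2 makes blinding one of its listed primary feasibility questions: "Whether it is possible to secure blinding of outcome assessors".

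The other relevant provisions are:

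- **PA interviews.** Section 6.7 has PAs asked at 24 and 48 weeks "which modules have been most, and least, useful; how or why". Section 7.1 repeats this for parts of the training. Sections 2.4 and 2.6 make PAs' health-promoting practice, measured by semi-structured interview, the primary intervention outcome.
- **Care-leaver interviews.** Section 6.7 asks care leavers "whether PAs have brought up topics covered in training modules".
- **Blinding check.** Outcome 3 (section 2.3) is "Ask assessors to record whether the interviewee has an intervention or control PA", as a forced choice, at 16, 32 and 48 weeks.
- **Operational rule.** Section 6.11 reads in full: "Peer researchers will not be told the allocation of the care leavers they interview".
- **Staffing.** Follow-up is done by study-team members, with peer researchers seeing care leavers where possible (6.6). A study-team member communicates allocation (6.5). Section 8.3.1 adds: "Some workshops will be observed by a member of the research team". Section 12.4 adds: "The research team include peer researchers who are full members of the Trial Management Group".
- **Database.** Section 11.3 provides for restricting access to information that may identify the treatment received.

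**The concern.** Section 3 asserts something that the interview content in sections 6.7 and 7.1 rules out for PAs. A reader of the results would take the primary intervention outcome as collected blind when it was not.

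For care leavers the issue is interpretation. Whether blinding can be secured is a question this study exists to answer, and Outcome 3 is its only stated measure. If the guess follows questions on module topics, the answers themselves may prompt it. A high share of correct guesses could then come from leaked allocation, which would be a problem for a definitive trial, or from the order of the interview, which is easily changed. The planned record holds no reason for the guess, so the two could not be told apart.

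**Working it through.** The protocol gives no blinding threshold and no sample size calculation, so there is no figure to reproduce. The check is mainly a comparison of sections, with illustrative arithmetic under stated assumptions.

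**1. PA interviews.** The section 3 claim and the section 6.7 questions concern the same visits. A question about which modules were useful presupposes training, so the answer shows the arm. Section 7.1 speaks of re-interviewing the same PAs directly after describing a questionnaire for the experimental arm only. If that means experimental-arm PAs alone, being interviewed already identifies the arm. Sections 6.6 and 7.3 suggest both arms, so the wording needs clarifying, but the contradiction stands on either reading. Section 6.11 does not cover whoever interviews PAs. Outcome 3 asks which kind of PA the interviewee has, so it covers care leavers only.

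**2. Timing of the guess.** Outcome 3: weeks 16, 32, 48. Follow-up assessments (sections 3, 6.1, 6.6): weeks 24, 48. Only week 48 is common to both. Week 24 has an assessment and no guess; weeks 16 and 32 have a guess and no outcome assessment.

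**3. Effect of cueing (illustration).** Let u be the assumed share of interviews in which the answers unmask the arm, with the remainder guessed at chance. The expected correct share is 0.5 + 0.5u. With 60 independent guesses (sections 3.3 and 6), the exact two-sided 5% cut-off above chance is 39 correct (upper-tail probability 0.014). With 48 guesses, that is 80% of 60, it is 32.

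| u | Expected correct | Chance of reaching 39/60 | Chance of reaching 32/48 |
|---|---|---|---|
| 10% | 55% | 8% | 7% |
| 20% | 60% | 26% | 21% |
| 30% | 65% | 56% | 47% |
| 40% | 70% | 84% | 75% |
| 50% | 75% | 97% | 93% |

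**4. Precision.** The approximate 95% half-width at 50% is 1.96 × √(0.25 × D / 60), where D = 1 + (m − 1) × ICC and m is care leavers per cluster.

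- No clustering: D = 1, giving 12.7 points.
- Six clusters (m = 10), assumed ICC 0.1: D = 1.9, giving 17.4 points.
- Twelve clusters (m = 5), assumed ICC 0.1: D = 1.4, giving 15.0 points.

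**5. Reach of one disclosure.** Assuming equal clusters and one assessor per cluster, learning one group's arm exposes that cluster's share of the 60.

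- Six clusters (Trial Summary): 10/60 = 17%.
- Nine (section 3.3, three groups at each of three authorities): 6.67/60 = 11%.
- Twelve (upper limit in section 3): 5/60 = 8%.

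**The case against.** The case for leaving the text alone has real substance on the care-leaver side.

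- **The questions are only a cue.** They cover general topics such as smoking, alcohol and nutrition and are put to the whole care-leaver sample. Control PAs already have a health role (sections 1.4 and 1.6), and nothing says that care leavers know their PA's arm. This stands.
- **Staffing.** A reader might infer that staffing reveals the arm, because team members communicate allocation and observe workshops, and peer researchers sit on the management group. The protocol does not say that the same individuals assess care leavers, or that allocation is discussed in that group. Sections 6.11 and 11.3 give partial safeguards. What remains is that overlap is permitted, since no section separates the roles.
- **Order of the guess.** This may be set in an interview guide or form that is not shown. That limits this part to a recommendation. It does not affect the PA contradiction or the mismatch in weeks.
- **Timing.** The two-monthly resource-use calls might fall near weeks 16 and 32. The protocol does not tie the guess to them.
- **Self-report.** The standardised care-leaver measures are self-reported, so assessor bias is limited to interviewer influence.
- **Process data.** The section 3 timetable labels PA follow-up as process and implementation data. Sections 2.4 and 2.6 nevertheless take the primary intervention outcome from PA interviews.

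A reader might also infer that the study could not answer its blinding question at all. That goes too far: a late guess would still show how aware assessors were under these procedures. It would blur the cause.

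**Conclusion.** The point holds in two parts of different strength. The section 3 claim is contradicted by sections 6.7 and 7.1 for PAs, on the kind of interview that supplies the primary intervention outcome. This rests on the text alone.

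For care leavers, blinding is possible but thinly protected. Outcome 3 is mis-timed against the assessments, and the protocol does not keep it apart from the cueing questions. The size of that effect is unknown because the share unmasked is an assumption; the table shows that 30% to 50% would probably look like failed blinding with 60 independent guesses. The 8% to 17% exposure depends on the number of clusters and on the equal-cluster, one-assessor assumption.

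Imperfect blinding is not itself an error here, since its feasibility is under test. The error is to assert it where the interview excludes it, and to fix its measure so that a poor result has no clear cause. The change should be made before follow-up starts.

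**What to change.** 1. In section 3, state that PA interviews are unblinded and confine the blinding claim to the care-leaver assessments. Clarify in sections 6.7 and 7.1 whether PAs in both arms are interviewed.
2. Fix the order of each care-leaver contact: standardised measures; then the arm guess and its reason; then the qualitative questions.
3. Set Outcome 3 at the 24- and 48-week assessments.
4. Extend section 6.11 to every care-leaver assessor and, within existing staff, use assessors who do not interview PAs, observe workshops or communicate allocation.

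The cost is a protocol edit, reordered forms with one added item, and slightly less flexible rostering. No extra participants or visits are needed.

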3.1 Project timetable

3.3 Planned recruitment rate

Personal Advisors

Participant personal advisors will be recruited from each of the participating local authorities. Whilst the local authority can require their staff to participate, and our aim is to recruit all PAs employed in the local authority, we intend to give personal advisors the option to withhold their consent to participate. In this feasibility study we are aiming to recruit from three groups of PAs at each of three local authorities.

Care Leavers

Participating care leavers will be recruited from each local authority until the target sample is reached (60 care leavers).

Recruitment will be proportionate to the size of the local authority and the flow of eligible care leavers and drawn equally from both arms of the study. We have not conducted a formal sample size calculation but are aiming to demonstrate the feasibility of a definitive RCT by recruiting around 20 care leavers at each of the three local authorities.

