6 TRIAL PROCEDURES

The study aims to recruit all Personal Advisors employed by the participating local authorities, and 60 Care Leavers, 30 from each arm of the trial. This section outlines the key trial procedures from identification of potential participants through to end of trial.

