6.2 STEP 2: Preliminary (eligibility) screening (Care Leavers) and expression of interest

Following an expression of interest from a care leaver, a member of the Research Team will arrange to meet with them to ascertain eligibility, ensure that they fully understand what they study will entail, that they are willing to proceed, and understand that they can withdraw at any time without giving any reason, and without

prejudice to the services they receive. This meeting may be online or in person, depending on circumstances.

The recruitment of Care Leavers will extend beyond the randomisation of PA groups until the training of PAs in the experimental group has been completed.

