14 ETHICAL AND REGULATORY CONSIDERATIONS

14.1 Governance and legislation

This trial will be conducted in accordance with:

- Conditions and principles of Good Clinical Practice (GCP)
- UK Policy Framework for Health and Social Care Research
- Data Protection Act 2018
- General Data Protection Regulation (GDPR)

Any amendments to the trial must be assessed and approved by the Sponsor prior to submission to the REC.

All recruitment will be undertaken by a member of the research team based in the University of Bristol.

This research trial will be conducted in accordance with conditions and principles of GCP. GCP is the international ethical, scientific, and practical standard to which all clinical research is conducted. Compliance with GCP provides public assurance that the rights, safety, and well-being of people taking part (trial participants) are protected and that research data are reliable.

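### Care leavers are to be enrolled equally by arm while recruitment runs across allocation, and the protocol gives no arm-blind way to reach that balance

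*Protocol*

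**What the plan says.** Section 3.3 sets the recruitment rule for these participants: "Recruitment will be proportionate to the size of the local authority and the flow of eligible care leavers and drawn equally from both arms of" […]. It also speaks of "recruiting around 20 care leavers at each of the three local authorities". Section 6 gives the aim as "60 Care Leavers, 30 from each arm of the trial".

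The timetable in Section 3 places care-leaver recruitment in months 2-6, randomisation of PA groups in months 5-6 and training in months 5-7. Under Section 6.5 (Step 5), randomisation is triggered by complete PA baseline data, not by complete care-leaver recruitment. Section 6.2 (Step 2) then says: "The recruitment of Care Leavers will extend beyond the randomisation of PA groups until the training of PAs in the experimental group has been completed". Section 6.4 (Step 4) says the same of care-leaver baseline data.

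Allocation is communicated to the local authority groups (Section 6.5). The local authority identifies and invites eligible care leavers (Section 6.2, overview), and Section 14.1 adds: "All recruitment will be undertaken by a member of the research team based in the University of Bristol". Blinding is described for those who collect follow-up data (Sections 3 and 6.11). Nothing similar is said of those who identify, invite or enrol.

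The number of PA groups is six in the Trial Summary, up to twelve in Section 3, and three at each of three authorities (nine) in Section 3.3.

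**The concern.** Care leavers enrolled before randomisation belong to groups that have no arm yet. If those groups turn out unequal between the arms, an equal draw can be restored only through the places filled after allocation. The protocol names no method that would do this without regard to arm: it sets no target per PA group and no randomisation restricted on the numbers already enrolled. The natural way to follow the rule is therefore to seek more care leavers from whichever arm is short.

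Two things are at stake. First, in a cluster trial that enrols individuals after allocation, knowledge of arm at invitation or enrolment is a known route to selection bias, and an arm-balance rule gives staff a reason to use that knowledge. Second, Section 2.2 asks whether a sample can be recruited and retained in each arm, and recruitment of care leavers is Outcome 1 in Section 2.3. Counts that have been steered towards equality say little about whether uptake differs by arm, which a feasibility trial should show before a definitive cluster trial is designed.

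**Working it through.** **The plan's own figure.** 3 authorities × 20 = 60 and 2 arms × 30 = 60, so the totals agree. There is no power calculation to reproduce (Section 10.1).

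**Places left after allocation.** The accrual pattern is not stated, so even accrual is assumed.
- Window of months 2-6 (5 months, 12 per month): allocation at the start of month 5 gives 3 × 12 = 36 before and 24 after; at the end of month 5, 48 before and 12 after.
- Window of months 2-7 (10 per month), if recruitment runs to the end of training: 30 after with allocation at the start of month 5, and 10 after with allocation at the end of month 6.
- With recruitment closing in month 6 and allocation at the end of month 6, no places remain. Section 6.2 (Step 2) does expect recruitment to go on after randomisation.

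**Nine groups (Section 3.3), equal flow per group.** 60/9 = 6.67 per group. The closest split is 4 groups against 5, giving 26.7 against 33.3.
- 36 before allocation: 4 per group, so 16:20. Reaching 30:30 needs the last 24 taken 14:10. Per group that is 14/4 = 3.5 against 10/5 = 2.0, a ratio of 1.75.
- 48 before allocation: 5.33 per group, so 21.3:26.7. The last 12 must be taken 8.67:3.33. Per group that is 2.17 against 0.67, a ratio of 3.25.

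**Six groups (Trial Summary), three per arm.** The expected split is 30:30, but nothing secures it. Treating the 36 early recruits as Binomial(36, 0.5), the arm gap is 6 or more with probability 0.41. The probability is higher if flow varies between groups: 0.50 to 0.61 for an assumed coefficient of variation of 0.3 to 0.5. A gap of 6 (21:15) needs the last 24 taken 9:15, a ratio of 15/9 = 1.7. Over all 60, exactly 30:30 arises by chance with probability 0.10.

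**What equal counts conceal.** Take the 24 post-allocation places, equal numbers invited per arm, and assumed consent of 60% against 40%. Left alone, the places fill 24 × 0.6/(0.6 + 0.4) = 14.4 against 9.6. Drawn equally they fill 12:12, and the difference shows only in the invitations needed: 12/0.6 = 20 against 12/0.4 = 30.

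**Price of unequal arms.** The standard error of an arm difference relative to 30:30, ignoring clustering, is √[(1/n₁ + 1/n₂)/(2/30)].
- 26.7:33.3 gives 1.006.
- 36:24 gives 1.021.
- 40:20 gives 1.061.

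**The case against.** Section 6 words the figure as something the study aims at. The only stopping rule in Section 3.3 is the overall total of 60, and nothing says that an arm closes at 30 or that a candidate is turned away because of arm. A reader might infer that the balance can be met only by enrolling with knowledge of arm. The documents do not support that: Section 3 aims for groups of comparable size, and six groups split 3:3 with ten care leavers each would give 30:30 under any allocation. Randomisation balanced on the numbers already enrolled could also achieve it. This stands. What remains is that the protocol adopts neither route, and that nine groups cannot be divided evenly.

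A reader might also infer that the rule hides any difference in recruitment between arms. That goes too far. Section 13.1 promises eligibility and consent percentages and a comparison of consenters with non-consenters, and Section 10.2 promises a CONSORT flowchart. These could show a difference if broken down by arm, and such a breakdown may properly sit in an analysis plan. The loss is confined to the enrolment counts.

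Much of the concealment risk comes from recruiting after allocation at all and would remain if the equal draw were deleted. That is also right; the rule adds to the risk and does not create it. Section 11.3 restricts database access to allocation for blinded staff, but does not say that recruiters are among them, and it cannot cover local authority staff who have been told.

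Finally, following flow and drawing equally by arm need not conflict if the first applies across authorities and the second within them. But with three groups in each authority, the nearest within-authority split that uses both arms is 2:1.

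**Conclusion.** The point holds as a defect in a stated recruitment rule. Sections 3.3 and 6 aim for equal enrolment by arm, recruitment runs across allocation, and the protocol offers neither an arm-blind route to that balance nor concealment from those who identify, invite or enrol.

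Under the nine-group plan, equal flow gives about 27:33, and moving to 30:30 would mean enrolment rates per group that differ 1.75-fold by arm after allocation, or 3.25-fold if 48 have already joined. These ratios rest on even accrual, equal flow per group, a 4:5 split and the aim being met exactly. None of these is fixed by the protocol, so the ratios illustrate scale and are not forecasts. The documents do not show that any care leaver would be refused because of arm.

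**What to change.** In Section 3.3, replace the equal-draw rule with care-leaver targets per PA group (or per authority), set before randomisation and left unchanged whatever arm a group receives. In Section 6, keep 30 per arm only as an expected number, so that the Section 2.2 objective retains a benchmark. Settle the number of groups at the same time, because the expected split depends on it. State that no invitation or enrolment decision may depend on arm; this matters most if targets are set per authority, since the mix of groups within an authority could still be steered. Commit to reporting eligible, invited and consented care leavers by arm, separately before and after allocation.

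The cost is a change of wording and some extra counting. Arms may be somewhat unequal, with the standard-error penalties shown above (under 1% at 27:33, about 2% at 36:24, 6% at 40:20, ignoring clustering), in a study that has no power calculation to protect. The change does not remove the selection risk of recruiting after allocation; it removes the incentive that the equal draw adds.
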